### 8.6.2. Sensitivity Analyses of the Primary Efficacy Results

Primary efficacy analysis will be based on the ITT population with a sensitivity analyses for efficacy based on the PP and Completers populations. A second analysis using the ITT population with subject-reported rather than investigator-confirmed attacks will also be conducted.

In addition, there will be 3 sensitivity analyses to examine the effect of missing data.

- 1. A missing data sensitivity analysis will be conducted in which observed data post study drug discontinuation are included in attack rate determination. The estimand for this analysis is referred to as the de facto estimand. Details on the determination of the attack rate are provided in Section 6.8.1.
- 2. A missing data sensitivity analysis will be conducted in which observed data post study drug discontinuation are used in combination with imputed data for subjects who discontinue study treatment prior to the end of Part 1 and do not continue to provide attack information. The method of imputation will depend upon whether the data are considered missing at random or not missing at random. Details on the imputation methodology are provided in Section 6.8.1.
- 3. A tipping point analysis will be conducted in which observed data post study drug discontinuation are combined with imputed data for subjects who discontinue study treatment prior to the end of Part 1 and do not continue to provide attack information. However, for this analysis the imputed attack rates will be multiplied by a factor,  $\delta$ , for subjects on active treatment. No such factor will be used for subjects on placebo treatment. The tipping point will be estimated as the value of  $\delta$  that tips the analysis to non-significant. It shows how much greater than expected the attack rate on active treatment would need to be for the missing data to alter the result of the analysis. Details are provided in Section 6.8.1.

A forest plot will be provided to visually compare the results obtained using first 2 methods of sensitivity analyses to the primary efficacy result.

## 8.7. Analysis of the Secondary Efficacy Endpoints

#### 8.7.1. Angioedema Quality of Life (Total and Domain Scores)

Change from baseline in AE-QoL questionnaire at Week 24 (total score) is a secondary endpoint for Part 1. Durability in AE-QoL questionnaire scores is a secondary endpoint for Parts 2 and 3.

The actual and change from baseline domain and total scores will be summarized by visit and treatment. For Part 1, changes from baseline in AE-QoL will be assessed with a MMRM model with fixed effects for treatment, baseline attack rate, baseline AE-QoL, visit, and a visit by treatment interaction and a random effect for subject. An unstructured covariance structure will be used. The estimated treatment difference comparing each active treatment to placebo at each post-baseline visit (Weeks 4, 6, 12, 18, and 24) will be displayed together with the 95% CI and the associated p-value. Least squares means (LSM) for each visit will also be presented with the standard error and the number of subjects contributing to the LSM. Total and domain scores will be listed for each subject and visit. The responses to the individual AE-QoL questions will also be listed.

Figures of mean actual and change from baseline AE-QoL total and domain scores will be produced with 1 line per treatment group. In addition, a cumulative distribution plot of AE-QoL Total Score at Week 24 will be provided.

Final analyses at the end of study will also include data from visits at Weeks 28, 32, 36, 48, 60, 72, 84, 96, and follow-up. Summaries will be updated to include the additional information. An additional descriptive summary of change from Week 24 will be provided for Part 2 and 3 visits for subjects originally randomized to placebo treatment.

A summary and analysis of the number and percent of subjects with at least a 6-point decrease (Minimum Clinically Important Difference [MCID]) in total AE-QoL score will be performed by visit for Part 1. The summary will be repeated at the end of the study. The analysis for Part 1 will be based on a logistic model with response of achievement of the MCID (yes/no), baseline attack rate and baseline AE-QoL total score as covariates and a fixed effect for treatment.

### 8.7.2. Number and Proportion of Days with Angioedema Symptoms

The number of proportion of days with angioedema symptoms through 24 weeks is a secondary endpoint for Part 1. The number and proportion of days with angioedema symptoms is also a secondary endpoint for Parts 2 and 3. Definitions of the endpoints are provided in Section 6.7.5.3.

For Part 1, the number and proportion of days with angioedema symptoms through Week 24 will be determined. Both the number and proportion of days will be summarized. The proportion of days with angioedema symptoms through Week 24 will be analyzed using an ANCOVA model with baseline attack rate as a covariate and treatment included as a fixed effect. The estimated treatment difference comparing each active treatment to placebo will be displayed together with the 95% CI and the associated p-value. LSMs will be presented with the standard error and the

number of subjects contributing to the LSM. The number and proportion of days with angioedema symptoms will be listed for each subject. A similar analysis will be conducted based on the effective dosing period, beginning on Day 8 and continuing through Week 24.

Final analyses at the end of the study will include a summary of the number and proportion of days with angioedema symptoms through Week 48 for those subjects originally randomized to active treatment and a summary through adjusted Week 24 for active treatment for subjects originally randomized to placebo. Only subjects who received at least 1 dose of study treatment in Part 2 of the study will be included in this summary. The subject listing will be updated to include the number and proportion of days with angioedema symptoms through Week 48. The number and proportion of days with angioedema symptoms during Part 3 of the study will be reported separately from Part 2.

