The number and proportion of days with angioedema symptoms through Week 24 will be computed. The proportion of days with angioedema symptoms through Week 24 will be analyzed using an analysis of covariance model with baseline attack rate as a covariate and treatment included as a fixed effect. The estimated treatment difference comparing each active treatment to placebo will be displayed together with the 95% CI and the associated p-value. Least squares means (LSM) will be presented with the standard error and the number of subjects who contribute to the LSM.

For the Investigator-confirmed HAE attacks during the effective treatment period, between-treatment comparisons will be performed using a Poisson regression model similar to that used for the primary endpoint analysis.

A combination of hierarchical testing and the Hochberg step-up procedure will be used to control the Type I error rate for testing of primary and secondary endpoints in Part 1.

Analysis of safety data for Parts 1, 2, and 3 and of effectiveness data for Parts 2 and 3 will primarily be descriptive.

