### 6.7.5.3. Number and Proportion of Days with Angioedema Symptoms

The number of days with angioedema symptoms is the sum of the days during the reporting period for which at least 1 symptom is reported during an investigator-confirmed HAE attack.

This endpoint will be determined for Parts 1 and 2 as investigator-confirmation will not be calculated for Part 3. As with the calculation of attack rate, if the subject discontinues treatment during the reporting period, any symptoms during confirmed attacks that occur within 24 hours after last dose will be counted in the calculation of days with angioedema symptoms and the additional 24-hour-period will be included in the duration of the reporting period.

The percentage of days with angioedema symptoms is derived as the number of days with angioedema symptoms divided by the duration of the treatment period of interest.

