# 8. EFFICACY

# 8.1. General Considerations

Data from all centers will be combined for analysis.

Hypothesis tests will be 2-sided. Hypotheses comparing each of the 2 active dose groups to placebo will be separately tested. Analyses of Part 2 data will be descriptive. No hypotheses will

be tested for Parts 2 and 3 nor will hypothesis testing be conducted to compare the 2 active dose groups.

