## 8.3. Statement of the Null and Alternate Hypotheses

Hypothesis testing will be conducted for Part 1 only. The primary null and alternative hypotheses, for each active dose separately, are:

- Ho: RA = RP; active treatment does not have a differential effect on the rate of investigator-confirmed HAE attacks
- $H_A: R_A \neq R_P$ ; active treatment does have a differential effect on the rate of investigator-confirmed HAE attacks

where  $R_A$  is the monthly attack rate for active treatment and  $R_P$  is the monthly attack rate for placebo treatment.

Secondary hypotheses are (in order of hierarchical testing):

- 1. AE-QoL
  - $H_0: \beta = 0$ ; active treatment does not have a differential effect on the change from baseline AE-QoL at Week 24
  - $H_A: \beta \neq 0$ ; active treatment does have a differential effect on the change from baseline AE-QoL at Week 24

where  $\beta$  is the parameter representing treatment effect for the dose of interest in a mixed-effects model with repeated measures (MMRM).

- 2. Proportion of days with angioedema symptoms
  - Ho:  $\beta = 0$ ; active treatment does not have a differential effect on the proportion of days with angioedema symptoms over the entire treatment period
  - HA:  $\beta \neq 0$ ; active treatment does have a differential effect on the proportion of days with angioedema symptoms over the entire treatment period

where  $\beta$  is the parameter representing treatment effect for the dose of interest in an analysis of covariance (ANCOVA) model.

- 3. Rate of investigator-confirmed HAE attacks during the effective treatment period (beginning on Day 8 through 24 weeks)
  - Ho: RA = RP; active treatment does not have a differential effect on the rate of investigator-confirmed HAE attacks during the effective treatment period
  - $H_A: R_A \neq R_P$ ; active treatment does have a differential effect on the rate of investigator-confirmed HAE attacks during the effective treatment period

where  $R_A$  is the monthly attack rate for active treatment and  $R_P$  is the monthly attack rate for placebo treatment during the effective treatment period.

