## 8.5. Multiple Comparisons and Multiplicity

There are 4 endpoints being tested. For each endpoint, there are 2 potential doses to be tested against placebo. The Type I error rate will be controlled at the study level by using a combination of hierarchical testing and the Hochberg procedure. The 4 endpoints will be tested in a hierarchical fashion, and the 2 doses will be tested using the Hochberg step-up procedure at each level of the hierarchy to which both doses progress through the hierarchy.

The first endpoint to be tested is the primary endpoint, the rate of investigator-confirmed HAE attacks during dosing in the entire 24-week treatment period of Part 1. Using the Hochberg step-up procedure, each of the 2 doses will be tested at the  $\alpha = 0.05$  level, comparing active treatment to placebo. If the maximum of the 2 p-values is < 0.05, the null hypotheses of no difference between the rate of attacks for subjects on active and placebo treatment will be rejected for both doses and testing will proceed to the next endpoint in the hierarchy with  $\alpha = 0.05$ . If the maximum of the 2 p-values is > 0.05 but the minimum of the 2 p-values is < 0.025, the null hypothesis for the dose with p < 0.025 will be rejected and testing for that dose only will proceed to the next endpoint in the hierarchy with  $\alpha = 0.025$ . Otherwise, the null hypotheses for both doses will not be rejected, testing will stop, and the next endpoint in the hierarchy cannot be tested.

The first, second, third, and fourth endpoints in the hierarchy are:

- 1. The rate of investigator-confirmed HAE attacks during dosing in the entire 24-week treatment period (Day 1 to Day 168)
- 2. Change from baseline in AE-QoL at Week 24 (total score)
- 3. Number and proportion of days with angioedema symptoms through 24 weeks
- 4. Rate of investigator-confirmed HAE attacks during dosing in the effective treatment period (beginning on Day 8 through 24 weeks)

The process described above will be continued for each endpoint in the hierarchy until either all 4 endpoints have been tested or testing has stopped due to non-rejection of the null hypotheses for both doses for endpoints earlier in the hierarchy. At each level of the hierarchy, the Hochberg step-up procedure is used to control Type I error rates if 2 doses are to be tested. Otherwise, if only 1 dose is being tested, the single test is conducted with  $\alpha = 0.025$ .

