All statistical tests will be 2-sided. Multiplicity adjustments for Part 1 analyses for the 2 dose groups are discussed in Section 8.5 along with handling of testing of multiple endpoints.

The Poisson model assumes that the mean and variance are equal. When the variance in the data is larger than the mean, the model is said to be over-dispersed. Over-dispersion is more likely to be a problem if a significant number of subjects have no attacks during the 24-week treatment period. As a sensitivity analysis to examine the appropriateness of the Poisson model, a negative binomial model will be used in place of the Poisson regression model. When the negative binomial dispersion parameter is equal to zero, the negative binomial and Poisson models are equivalent. If the results of the model obtained using the negative binomial distribution are similar to that of the model that assumes the Poisson distribution and a statistical test of the dispersion parameter does not show that it is significantly greater than zero, the Poisson model will remain as the primary model for analysis.

Plots of mean confirmed attack rate by month and scatter plots of baseline attack rate vs. 24-week attack rate will be produced with a different color for each treatment. Plots of mean attack rate per month will be updated to include the Part 2 data at the end of the study. Adjusted subject-reported attack rate data per month will be plotted separately for Part 3, as Part 3 does not include investigator confirmation of attacks.

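### SAP 8.7.2's ANCOVA for symptom days makes no allowance for unequal variances: if spread falls as a dose works, both CIs under-cover when both doses work about equally, and a weaker dose's p-value is too small

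*SAP*

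**What the plan says.** SAP 6.7.5.3 counts a symptom day only if it falls within an investigator-confirmed attack. The proportion "is derived as the number of days with angioedema symptoms divided by the duration of the treatment period of interest". For Part 1, SAP 8.7.2 states that this proportion "will be analyzed using an ANCOVA model with baseline attack rate as a covariate and treatment included as a fixed effect", and then: "The estimated treatment difference comparing each active treatment to placebo will be displayed together with the 95% CI and the associated p-value". The summary at the front of the SAP gives the same model. SAP 8.7.2 asks for a similar analysis of the effective dosing period, from Day 8 through Week 24.

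SAP 8.5 places "Number and proportion of days with angioedema symptoms through 24 weeks" third of four endpoints, with the Hochberg procedure across the two doses at each level that both reach.

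On the number of models, SAP 8.3 says that β "is the parameter representing treatment effect for the dose of interest in an analysis of covariance (ANCOVA) model", and SAP 8.1 says: "Hypotheses comparing each of the 2 active dose groups to placebo will be separately tested". Neither says outright whether one three-arm model or one model per dose is fitted. One model with a three-level factor is the natural reading. SAP 8.7.2 takes both comparisons from a single model, and the example code for the primary endpoint in SAP 8.6.1 has one treatment class variable and no restriction to pairs of arms.

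No arm-specific variance, robust standard error, transformation or non-parametric check is given for this endpoint. SAP 8.2, on statistical assumptions, lists only baseline summaries. The negative binomial check in SAP 8.6.1 covers the primary endpoint only. The protocol supplied is for Study BCX7353-202 and the SAP for Study BCX7353-302, so the protocol cannot settle the point.

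**The concern.** The proportion of symptom days is bounded at zero and built from the same attacks as the primary endpoint. For those attacks the SAP adopts a model in which spread is tied to level: "The Poisson model assumes that the mean and variance are equal". It also contemplates that many subjects may have no attacks; each of them scores exactly zero here. If a dose works, a smaller spread in its arm is the natural consequence.

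An ordinary three-arm ANCOVA estimates one residual variance over all arms. A low-variance arm then lowers the standard error of every comparison with placebo, including that of the other dose. At stake are the coverage of the reported intervals and the p-value of the weaker dose, for an endpoint that carries a confirmatory claim.

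**Working it through.** **Inputs from the SAP.** Allocation 1:1:1 (4.4.1); 40 per arm (4.3.1); two-sided tests (8.1); planning reduction 50%, and a 73.8% reduction observed in the earlier study (4.3.1).

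**The plan's own figure.** SAP 4.3.1 states 94% power for 32 per arm, difference 0.5, SD 0.55. The normal approximation is 0.5 / (0.55 × sqrt(2/32)) = 3.64, and 3.64 − 1.96 = 1.68, giving 95.3%. The noncentral t with 62 df gives 94.7%. The figure is reproduced, and 32 / 0.8 = 40. It concerns attack rate under a common SD. The SAP gives no operating figure for symptom days.

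**Standard error ratio.** Let vP, v1 and v2 be the residual variances, with n per arm.
- True variance of dose 1 minus placebo: (vP + v1)/n.
- Three-arm model: (2/n) × (vP + v1 + v2)/3.
- Model SE / true SE = sqrt[(2/3)(vP + v1 + v2)/(vP + v1)].

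The ratio is below 1, and the interval too narrow, only if 2·v2 < vP + v1. A two-arm fit at 1:1 uses (2/n) × (vP + v1)/2, which equals the true variance. Coverage is 2Φ(1.96 × ratio) − 1, and the size for an inert dose is one minus that.

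**Results**, with vP = 1 and variance assumed proportional to the mean / to the mean squared:

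| True reductions (dose 1, dose 2) | SE ratio, dose 1 | Coverage, dose 1 | Coverage, dose 2 |
|---|---|---|---|
| 0%, 0% | 1.000 / 1.000 | 95.0% / 95.0% | 95.0% / 95.0% |
| 0%, 50% | 0.913 / 0.866 | 92.6% / 91.0% | 96.1% / 96.8% |
| 0%, 73.8% | 0.868 / 0.830 | 91.1% / 89.6% | 96.8% / 97.4% |
| 30%, 50% | 0.929 / 0.882 | 93.1% / 91.6% | 94.7% / 94.1% |
| 50%, 50% | 0.943 / 0.894 | 93.5% / 92.0% | 93.5% / 92.0% |
| 73.8%, 73.8% | 0.897 / 0.842 | 92.1% / 90.1% | 92.1% / 90.1% |

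Worked line for 0%, 50%, variance proportional to the mean: sqrt[(2/3)(1 + 1 + 0.5)/(1 + 1)] = sqrt(0.833) = 0.913. Size is 2[1 − Φ(1.96 × 0.913)] = 7.4%. With variance proportional to the mean squared it is 9.0%.

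**Simulation**, 40 per arm, ANCOVA with baseline rate, no dropout, two sets of assumptions:
- Set A: gamma-distributed monthly rates, mean 2.5-3, CV 0.6-0.8, 2-2.5 days per attack; 8,000 trials per scenario.
- Set B: 3.8 attacks per 28 days (from SAP 4.3.1: 0.70/0.738 = 0.949 per week, times 4), Poisson or gamma-Poisson counts, 2 days per attack; 6,000 trials per scenario.

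| Scenario | Pooled, A | Pooled, B | Robust SE, A (HC2) | Robust SE, B (HC3) | Two-arm, B |
|---|---|---|---|---|---|
| Inert dose, other −50%: rejection | 7.5-7.6% | 6.9-7.2% | 5.0-5.6% | 4.0-4.7% | 4.6-5.1% |
| Inert dose, other −74%: rejection | 8.2-9.5% | 8.2-9.1% | 5.0-5.6% | 4.9-5.1% | 5.2-5.3% |
| Both −50%: coverage | 93-94% | 91.8-93.9% | 94.5-95.4% | 94.9-95.7% | 94.5-95.5% |
| Both −74%: coverage | 91-92% | not run | 94.5-95.4% | not run | not run |

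The HC2 ranges in set A span both effect sizes. With both doses null, both methods held 4.5-5.1%. In set B a 50% cut took the SD from 0.064 to 0.045 (Poisson) and from 0.168 to 0.090 (gamma-Poisson). These are variance ratios of 0.49 and 0.29, inside the 0.5 to 0.25 range of the formula.

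**The case against.** **Gating.** A reader might infer that the study's Type I error rises to 7-9.5%. The documents do not support this. Under SAP 8.5 a dose reaches this test only after rejection on attack rate and on AE-QoL. For a dose inert on everything, the chance of rejecting here cannot exceed the chance of rejecting AE-QoL, about 5% if that test holds its level. The remaining route needs a dose that truly improves attack rate and AE-QoL but not symptom days, which is implausible when symptom days are counted only within attacks. This objection stands. It does not repair the intervals of doses that do pass.

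**Direction.** A reader might also infer that every interval is too narrow. That is not so: beside an inert dose the effective dose's interval is slightly too wide, and under the global null nothing is distorted.

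**Inferred premises.** The single three-arm model is the natural reading but is not stated, and separate two-arm fits largely remove the distortion. The falling variance is not documented either. The only SD in the SAP is a common one for attack rate (4.3.1), under which the ratio is 1.000. That SD is a planning assumption based on a pooled estimate. It is not evidence of equal variances, and it sits uneasily with the primary Poisson model.

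**A strained scenario.** The 73.8% was observed at the equivalent of 110 mg, the lower dose here. Pairing it with an inert dose requires 150 mg to be inert while 110 mg works, or 110 mg to be inert against the one prior result that the SAP reports. The cases with both doses effective are the realistic ones.

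**Conclusion.** The point holds in a limited form. If one three-arm ANCOVA is fitted and variance falls with the mean, both intervals under-cover when both doses work about equally: about 92-94% at a 50% cut and 91-92% at 74%. When the other dose is stronger, the weaker dose's interval is too narrow and its p-value too small, with an ungated test size of about 7-9% if it is inert. The effective dose beside an inert one gets about 96-97% coverage. The main damage is to the reported intervals and the weaker dose's p-value; study-wise Type I inflation is small. The size depends on assumed attack rates, between-subject variation and days per attack, and on no dropout, although SAP 4.3.1 allows for 20%. The correction is worth making because it costs so little.

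**What to change.** In SAP 8.7.2, keep the mean model (treatment and baseline attack rate) and add one sentence: a separate residual variance is estimated for each arm (PROC MIXED with REPEATED / GROUP=treatment and Satterthwaite or Kenward-Roger degrees of freedom), or HC2/HC3 standard errors are used. Apply the same to the Day 8 to Week 24 analysis, and say whether one model or one per dose is fitted.

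The cost is a line of text and one option in the code. When both doses halve attacks, intervals widen by about 6% (1/0.943 = 1.06) if variance follows the mean, or 12% (1/0.894 = 1.12) if it follows the mean squared. Where variances are equal, almost nothing is lost.

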## 6.6.1. Baseline Attack Rate

Enrollment into treatment groups is stratified by the baseline HAE attack rate as determined by the IXRS system based on the number of attacks and duration of screening as input by the sites ( $\geq 2$  attacks/month vs. < 2 attacks/month). For analysis purposes, the baseline attack rate will be calculated from the diary data and expressed as attacks per month where 1 month = 28 days as follows:

Number of HAE attacks meeting baseline criteria from Screening to First Dose Date/time × 28

Date of First Dose – Screening Date + 1

Criteria that must be met for attacks to qualify for confirmation by the Investigator during the baseline period are provided in Section 4.1.

Baseline attack rate will be included in statistical models as appropriate.

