# 7.9. Baseline Primary and Secondary Efficacy Evaluations

All attacks will be listed. The baseline attack rate and the categorized baseline attack rate will be summarized by Part 1 treatment using descriptive statistics for baseline attack rate and n [%] for the categorized baseline attack rate. The proportion of days with HAE symptoms will also be included in the summary.

Similarly, a summary of baseline of AE-QoL total and domain scores will be provided by Part 1 treatment.

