#### 17. **APPENDIX**

# **17.1.** Table of Contents for Data Display Specifications

Output #	Population	Output Title
14.1.1.1	ITT	Summary of Subject Disposition by Country and Site, Part 1
14.1.1.1.ES	ITT	Summary of Subject Disposition by Country and Site, Entire Study
14.1.2.1	ITT	Summary of Analysis Populations
14.1.2.2	ITT	Summary of Subgroups
14.1.2.3.1	ITT	Summary of Inclusion/Exclusion Criteria Deviations
14.1.2.3.2	Screen Failures	Summary of Inclusion/Exclusion Criteria Deviations
14.1.2.4	ITT	Summary of Protocol Deviations, Part 1
14.1.2.4.ES	ITT	Summary of Protocol Deviations that Occurred During Part 2
14.1.2.5	ITT	Summary of Confirmation of Diagnosis of HAE Type I or II
14.1.3.1.1	ITT	Summary of Demographic Characteristics
14.1.3.1.1.ES	ITT	Summary of Demographic Characteristics - Subjects Who Transitioned to Part 2
14.1.3.1.2	РР	Summary of Demographic Characteristics
14.1.3.1.3	Screen Failures	Summary of Demographic Characteristics
14.1.3.2	ITT	Summary of Subject-Reported HAE Baseline Characteristics - HAE Medical History
14.1.3.3	ITT	Summary of Past Prophylactic Treatments of HAE
14.1.3.4	ITT	Summary of Current On-Demand Treatments of HAE
14.1.3.5	ITT	Summary of Subject-Reported HAE Baseline Characteristics – Primary Acute Attack Treatment Information
14.1.3.6	ITT	Summary of Pre-Treatment Investigator-Confirmed Attack Rates and Angioedema Symptoms
14.1.4.1	ITT	Summary of Medications Taken within 30 Days of Screening and Discontinued Prior to Dosing
14.1.4.2	ITT	Summary of Concomitant Medications, Part 1
14.1.4.2.ES	ITT	Summary of Concomitant Medications – Entire Study
14.1.4.3	ITT	Summary of Concomitant Medications for HAE, Part 1
14.1.4.3.ES	ITT	Summary of Concomitant Medications for HAE, Entire Study
14.1.4.3.P3	ITT	Summary of Concomitant Medications for HAE, Part 3
14.1.4.4	ITT	Summary of Concomitant Medications for HAE – Attack Level, Part 1
14.1.4.4.ES	ITT	Summary of Concomitant Medications for HAE – Attack Level, Entire Study
14.1.4.4.P3	ITT	Summary of Concomitant Medications for HAE – Attack Level, Part 3
14.1.5.1	Safety	Summary of Treatment Exposure and Treatment Compliance, Part 1
14.1.5.1.ES	Safety	Summary of Treatment Exposure and Treatment Compliance, Entire Study
14.2.1.1	ITT	Summary of Hierarchical Testing for Efficacy Endpoints
14.2.1.2.1	ITT	Overall Attack Summary During Part 1
14.2.1.2.1.ES	ITT	Overall Attack Summary During Entire Study
14.2.1.2.2	РР	Overall Attack Summary During Part 1

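### The ANCOVA for days with angioedema symptoms (SAP 8.7.2) leaves out the endpoint's own run-in value: a valid test, with an avoidable loss of precision

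*SAP*

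**What the plan says.** SAP 8.7.2 states that the proportion of days with symptoms through Week 24 is "analyzed using an ANCOVA model with baseline attack rate as a covariate and treatment included as a fixed effect", with a similar analysis for the effective dosing period. The statistical methods part of the SAP's Technical Summary Report gives the same two-term model. Section 8.5 places "Number and proportion of days with angioedema symptoms through 24 weeks" third in the hierarchy.

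Section 6.7.5.3 defines the number of days as "the sum of the days during the reporting period for which at least 1 symptom is reported during an investigator-confirmed HAE attack"; dividing by the length of the period gives the proportion. The covariate is built differently. In 6.6.1 its numerator is "Number of HAE attacks meeting baseline criteria from Screening to First Dose Date/time", multiplied by 28 and divided by days from screening to first dose.

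The run-in version of the endpoint is already planned as a baseline description. Section 7.9 says "The proportion of days with HAE symptoms will also be included in the summary", and Table 14.1.3.6 in section 17.1 is titled "Summary of Pre-Treatment Investigator-Confirmed Attack Rates and Angioedema Symptoms".

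For comparison, the AE-QoL model in 8.7.1 has "fixed effects for treatment, baseline attack rate, baseline AE-QoL, visit, and a visit by treatment interaction". The EQ-5D-5L, TSQM and WPAI models (9.1 to 9.3) likewise carry a baseline attack term and the outcome's own baseline.

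**The concern.** Days with symptoms are, roughly, the number of attacks times the days per attack. If some subjects typically have long attacks and others short ones, and this persists from run-in into treatment, it drives the outcome. Baseline attack rate cannot account for it, because two subjects with the same rate can have quite different burdens of symptom days. Under the planned model that stable difference stays in the residual and widens the confidence interval. The run-in proportion carries the missing information and is already being derived.

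At stake is the power of a test inside the Type I error hierarchy. A dose that fails here does not go on to the fourth endpoint. The SAP states no power, SD or effect size for this endpoint.

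**Working it through.** **1. The plan's own figure.** SAP 4.3.1 uses 32 per arm, difference 0.5, SD 0.55, two-sided 0.05.

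Power = Φ(0.5/0.55 × √(32/2) − 1.960) = Φ(3.636 − 1.960) = Φ(1.676) = 95.3%. The noncentral t with 62 df gives 94.7%. The SAP states 94%, so it reproduces closely. Dropout of 20% gives 32/0.80 = 40 per arm, also as stated. Both figures concern attack rate, not symptom days.

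**2. Effect of a second covariate in general.** If r is the partial correlation of the run-in proportion with the outcome, given attack rate, residual variance is multiplied by 1 − r², and

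power = Φ((z₁₋α/₂ + z_power)/√(1 − r²) − z₁₋α/₂).

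For example, from 80% with r = 0.5: 2.802/√0.75 = 3.235; 3.235 − 1.960 = 1.275; Φ(1.275) = 89.9%. The documents give no value for r, so a range is shown (two-sided 0.05):

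| r | from 80% | from 94% |
|---|---|---|
| 0 | 80% | 94% |
| 0.2 | 81.6% | 94.8% |
| 0.3 | 83.6% | 95.8% |
| 0.4 | 86.4% | 97.0% |
| 0.5 | 89.9% | 98.2% |
| 0.6 | 93.8% | 99.3% |

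**3. Simulation with attack length made explicit.** Taken from the SAP: 40 per arm, at least 2 run-in attacks, 168 days. Assumed:
- attack rate gamma, mean 3 per 28 days, CV 0.6;
- mean attack 2.5 days, attack-level CV 0.5, minimum 1 day;
- on-study rate frailty CV 0.4;
- run-in of 28, 42 or 56 days;
- attack length carries over from run-in to treatment.

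The last two columns show the variance cut with these run-ins, and with every subject randomized at the earliest day that SAP 4.1 allows (Day 14 with 3 attacks, Day 28 with 2). Power is for 35% fewer attacks on drug.

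| Between-subject CV of attack length | Power, attack rate only → run-in proportion added | Variance cut | Variance cut, earliest randomization |
|---|---|---|---|
| 0 | 83% → 83% | 0% | about 0% |
| 0.3 | 76% → 80% | 11% | 7% |
| 0.5 | 62% → 76% | 26% | 18% |
| 0.7 | 54% → 73% | 38% | 29% |

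As sample size, a cut of v is worth 40/(1 − v) per arm under the planned model: 40/0.93 = 43 to 40/0.89 = 45 at CV 0.3; 40/0.82 = 49 to 40/0.74 = 54 at CV 0.5; 40/0.71 = 56 to 40/0.62 = 65 at CV 0.7.

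**4. At the planned effect.** SAP 4.3.1 plans on a 50% reduction in attack rate. There the gain is about 1 to 3 points for a CV of 0.3 to 0.5 and about 8 to 10 points at 0.7. A second simulation with a simpler model (no on-study frailty, run-in of 28 to 56 days set by the subject's rate, 800 replicates) gives the same pattern:

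| CV | 50% fewer attacks | 40% fewer | 30% fewer |
|---|---|---|---|
| 0 | 100% → 100% | 99.9% → 99.8% | 88.4% → 87.5% |
| 0.3 | 99.9% → 100% | 95.9% → 98.0% | 72.9% → 78.8% |
| 0.5 | 96.4% → 99.5% | 83.0% → 93.6% | 56.1% → 73.6% |
| 0.8 | 86.0% → 99.0% | 61.8% → 89.5% | 36.2% → 65.8% |

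The simulation standard error near 95% is √(0.95 × 0.05/800) = 0.8 points, so differences of a point or so are not distinguishable from none.

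**5. Cost.** With 3 × 40 = 120 subjects, the planned model estimates an intercept, two treatment effects and one slope: 120 − 4 = 116 residual df. Adding the covariate leaves 115.

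**The case against.** **The planned test is valid.** It is, and this stands. Randomization protects the comparison, and the model already holds a prespecified prognostic covariate. A reader might infer bias or Type I error inflation; nothing in the SAP supports that.

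**The gain is small at the planned effect.** This largely stands. At a 50% reduction power is already high unless attack length varies a great deal between subjects, and SAP 4.3.1 cites an observed 73.8% reduction at the dose equivalent to 110 mg. A reader might take the 35% column as the expected loss; the SAP does not plan on 35%. The narrower interval remains whatever the power.

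**A short run-in makes the covariate noisy.** True in part. With everyone randomized at the earliest permitted day, the variance cut falls to about 7%, 18% and 29% at CVs of 0.3, 0.5 and 0.7. It does not vanish. Much smaller cuts (about 2%, 6% and 11%) have been suggested for this case, but they did not reproduce.

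**The questionnaire models are the wrong comparators.** This stands in part. Days with symptoms is an on-treatment proportion, not a change score. The other attack-derived analyses (the primary model in 8.6.1, the effective-period rate in 8.7.3, the responder regression in 8.8.2) adjust for baseline attack rate only. It would be too strong to say that 8.7.2 breaks a rule of the SAP. But attack rate is the natural baseline for an attack count or rate; for symptom days it is only half of the baseline.

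**Little is lost if the fourth endpoint is blocked.** Fair. That endpoint is the primary rate without the first week, and the third is reached only after the first two succeed.

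**The covariates may come from the Study 302 protocol.** That protocol is not among the documents (the protocol supplied is for Study 202), so this cannot be checked.

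**Conclusion.** The point holds as a loss of precision that costs almost nothing to avoid. The model for the third endpoint in the hierarchy omits a baseline that is already to be derived and that carries information on attack length which attack rate lacks. Adding it cuts residual variance by about 0% if subjects do not differ in typical attack length, 7-11% at a between-subject CV of 0.3, 18-26% at 0.5 and 29-38% at 0.7. The lower end of each range is for the earliest permitted randomization. Power rises by about 1 to 3 points at the planned 50% reduction for CVs of 0.3 to 0.5, and by about 8 to 10 points at 0.7. If the true reduction is nearer 35%, the rise is about 3 to 19 points.

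These sizes rest on an attack-length CV that the documents do not give, on attack length carrying over from run-in to treatment, and on the assumed rate and duration distributions. The direction does not depend on the exact values: the gain is nil at worst, for one degree of freedom.

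**What to change.** Before Part 1 is unblinded, amend SAP 8.7.2, and the matching sentence in the Technical Summary Report, so that the ANCOVA includes the baseline proportion of days with symptoms alongside baseline attack rate. Apply this to both the entire and the effective dosing period. Keep baseline attack rate in the model.

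State the derivation, since 6.7.5.3 defines the endpoint for Parts 1 and 2 but not for the run-in: days from screening to first dose with at least one symptom during a confirmed attack, under the same confirmed-attack rule, divided by the days in that period.

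The cost is one covariate, one degree of freedom of about 116, and no new data. Made after unblinding, the same change would be post hoc.
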